[figure not shown]

# ClinicalTrials.gov Results Data Element Definitions for Interventional and Observational Studies

## ▼1. Participant Flow

Enrollment

Arms	Assigned Interventions

Experimental: Neuromuscular Electrical Stimulation (NMES) with TDT
	
Device: Procedure: Neuromuscular Electrical Stimulation with TDT
 
The skin to be treated will be cleaned and dried. NMES will be implemented with signals received from two channels. In the first channel, the upper electrodes will be placed horizontally just above the hyoid bone. This is the place where the cupping is felt when the finger is pressed right under the chin. In the second channel, the lower electrodes will be placed horizontally, just above the thyrohyoid muscle. This is the place where you can feel a cupping when pressed with your finger, on both sides of the apple in the larynx. The device will be set to start at the lowest power, with very short pulses of approximately 700 microseconds, at intervals of 1 second. The power will be gradually increased according to the device and the power that the patient feels vibration will be stopped. The power to be applied will not exceed 25 milliamps. NMES application and Traditional Dysphagia Therapy will be applied for 45 minutes a day, 5 days a week for 3 weeks.

Active Comparator: Traditional Dysphagia Therapy (TDT)
	
Behavioral: Procedure: Traditional Dysphagia Therapy (TDT)
 
Traditional dysphagia therapy includes diet modification training, teaching postural compensatory methods, training of oral motor control exercises and tongue root exercises, training of swallowing maneuvers, and practice of chin-resistance exercise, which is the exercise of opening the upper esophageal sphincter.
 
Traditional Dysphagia Therapy will be applied for 45 minutes a day, 5 days a week for 3 weeks.

### Period(s) \*

Our study was created by planning a 3-month follow-up period. Information about the number of patients at the beginning and end of the study will be reported when the study is completed. Definition: Discrete stages of a clinical study during which numbers of participants at specific significant events or points of time are reported.

### ▼2. Baseline Characteristics

Patients' age, gender, educational status, height and weight, additional diseases, medications used, time after the patient's stroke, duration of hospitalization in the acute period after stroke, stroke type (ischemic / hemorrhagic), lesion region, degree of ambulation according to functional ambulation classification will be recorded at the beginning of the study.

Arms	Assigned Interventions

Experimental: Neuromuscular Electrical Stimulation (NMES) with TDT
	
Device: Procedure: Neuromuscular Electrical Stimulation with TDT
 
The skin to be treated will be cleaned and dried. NMES will be implemented with signals received from two channels. In the first channel, the upper electrodes will be placed horizontally just above the hyoid bone. This is the place where the cupping is felt when the finger is pressed right under the chin. In the second channel, the lower electrodes will be placed horizontally, just above the thyrohyoid muscle. This is the place where you can feel a cupping when pressed with your finger, on both sides of the apple in the larynx. The device will be set to start at the lowest power, with very short pulses of approximately 700 microseconds, at intervals of 1 second. The power will be gradually increased according to the device and the power that the patient feels vibration will be stopped. The power to be applied will not exceed 25 milliamps. NMES application and Traditional Dysphagia Therapy will be applied for 45 minutes a day, 5 days a week for 3 weeks.

Active Comparator: Traditional Dysphagia Therapy (TDT)
	
Behavioral: Procedure: Traditional Dysphagia Therapy (TDT)
 
Traditional dysphagia therapy includes diet modification training, teaching postural compensatory methods, training of oral motor control exercises and tongue root exercises, training of swallowing maneuvers, and practice of chin-resistance exercise, which is the exercise of opening the upper esophageal sphincter.
 
Traditional Dysphagia Therapy will be applied for 45 minutes a day, 5 days a week for 3 weeks.

### Overall Number of Baseline Participants \*

A total of 38 patients were planned to be included in the study, including 19 in each group.

### Baseline Measure Information \*

Patients' age, gender, educational status, height and weight, additional diseases, medications used, time after the patient's stroke, duration of hospitalization in the acute period after stroke, stroke type (ischemic / hemorrhagic), lesion region, degree of ambulation according to functional ambulation classification will be recorded at the beginning of the study. The change in Functional Oral Intake Scale (FOIS) will be our primary outcome measure in our research.

## Baseline Measure Title \*

Definition: The name of the baseline or demographic characteristic measured in the clinical study. Select as many as needed.

- Study-Specific Measure \* § *(Select as many as needed)*
- Age \* *(Select at least one of the following):*
  - Age, Continuous: For example - mean or median age
- Sex/Gender \* *(Select at least one of the following):*
  - Sex: Female, Male
- Race and Ethnicity \* §
  - Race and Ethnicity Not Collected

## Measure Type \*

Count of Participants

## Measure of Dispersion \*

Not Applicable (only if Measure Type is "Number", "Count of Participants", or "Count of Units")

## Baseline Measure Data \*

When the investigation is completed, information about each baseline measures data will be updated.

## Unit of Measure \*

height (cm) and weight (kg)

### ▼3. Outcome Measures

#### Primary Outcome Measure:

- Change in Functional Oral Intake Scale (FOIS)

Functional Oral Intake Scale (FOIS) is a scale that shows the functional oral intake of patients with dysphagia. FOIS used for evaluation is a two part scale consisting of 7 levels. It is used to show whether the individual is dependent on the feeding tube and the level of oral intake. On this scale, 7 shows the best and 1 shows the worst functional oral intake. The change in FOIS will be our primary outcome measure in our research. It has been evaluated as an appropriate tool to demonstrate the change in functional oral intake in stroke patients. It is suitable as an independent measure of functional oral intake in prospective studies of stroke-related dysphagia.

[Time Frame: before intervention, immediately after intervention, 3 months after the intervention]

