### Measure of Dispersion/Precision \*

80% Confidence Interval

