### Statistical Analyses [\*]

The required sample size was determined by power analysis based on previous studies. [G \* Power, Version: 3.1.9.2 Statistical Packages, Power Analysis for Repeated (ANOVA) Type 1 error probability was 0.05%, power of the test was 80%.] The minimum required number of people for each group was calculated as 17. It was predicted that 10% of the patients would be excluded during the study, and a total of 38 patients were planned to be included in the study, including 19 in each group.

Descriptive statistics of numerical variables will be given as mean, standard deviation, median, minimum and maximum. Descriptive statistics of qualitative variables will be given as numbers and percentages. Whether numerical variables show normal distribution will be investigated with Shapiro Wilk test.

In the comparison of two independent groups, Student's t test will be used for variables with normal distribution and Mann Whitney U test will be used for non-normally distributed variables. In comparing two dependent groups, Paired t test will be used for variables with normal distribution and Wilcoxon test will be used for non-normally distributed variables. A statistical significance level of 0.05 will be taken,  $p < 0.05$  will be considered statistically significant. SPSS package program will be used in calculations.

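### Change in FOIS, the only primary outcome, is assessed at two follow-ups with no deciding visit, assigned test or multiplicity rule; counting either visit as success would give about 7.0% to 9.1% false positives instead of 5% (assumed correlation 0.9 to 0.5).

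*Combined protocol and SAP*

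**What the plan says.** The Baseline Measure Information entry states "The change in Functional Oral Intake Scale (FOIS) will be our primary outcome measure in our research", and the Primary Outcome Measure entry repeats it: "The change in FOIS will be our primary outcome measure in our research". No other primary outcome is listed. The schedule for FOIS is "Time Frame: before intervention, immediately after intervention, 3 months after the intervention", so each patient contributes two changes from baseline. The Period(s) entry in section 1 adds only that follow-up lasts three months.

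The whole analysis plan is in the Statistical Analyses section. For comparisons between arms it says "In the comparison of two independent groups, Student's t test will be used for variables with normal distribution", with Mann-Whitney otherwise. For comparisons within an arm it says "In comparing two dependent groups, Paired t test will be used for variables with normal distribution", with Wilcoxon otherwise. The threshold is "A statistical significance level of 0.05 will be taken". The section does not mention FOIS, a visit or multiplicity.

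The sample-size sentence in the same section reads "Power Analysis for Repeated (ANOVA) Type 1 error probability was 0.05%, power of the test was 80" (per cent). It gives 17 per group, raised to 19 for 10% loss. The repeated-measures ANOVA appears only there and is not among the planned analyses. The Measure of Dispersion/Precision entry in section 3 reads "80% Confidence Interval".

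**The concern.** Listing several assessment times is normal. The difficulty is that the between-arm rule, applied to the primary outcome as written, produces two tests of equal standing, each at 0.05. If they disagree, the plan has no rule for the verdict, and the deciding visit can be chosen once both results are known. A p-value below 0.05 chosen in that way no longer carries a 5% error rate. The trial has 38 patients and a single primary outcome, so nothing else in the plan would settle the matter.

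**Working it through.** **1. The plan's own figure.** The inflation step reproduces: 17 / 0.9 = 18.9, so 19 per group and 38 in total. The 17 cannot be reproduced, because the effect size, number of measurements, correlation and tested effect are not given. It is attainable: with an assumed f = 0.25, correlation 0.5, two measurements and the group-by-time test, a total of 34 gives 80.7% power and 32 gives 78.1%. This does not show what was actually done.

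**2. Inputs for the error rate.** From the plan: two follow-ups and a 0.05 level for each test. Assumed: two-sided tests (sidedness is not stated), approximately normal test statistics, and a correlation ρ between the two changes. The documents give no ρ, so a range is shown.

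**3. False-positive rate if either visit counted.** With no treatment effect,

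P(either) = 0.05 + 0.05 − P(both significant).

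| ρ | P(both) | P(either) |
|---|---|---|
| 0 | 0.0025 | 0.0975 |
| 0.5 | 0.0093 | 0.0907 |
| 0.7 | 0.0165 | 0.0835 |
| 0.9 | 0.0296 | 0.0704 |
| 1 | 0.0500 | 0.0500 |

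The rate is 7.0% to 9.1% for ρ from 0.9 to 0.5, and 5% to 9.75% over the full range from 1 to 0.

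**4. How often the choice of visit would matter.** Take the same true effect at both visits, large enough for 80% power at each. Each statistic then has mean 1.96 + 0.84 = 2.80, and

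P(exactly one significant) = 2 × (0.80 − P(both)).

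For a t test with 17 per group, 80% power corresponds to 0.99 SD of change. The plan states no effect, so this is an assumption. The last column simulates those t tests.

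| ρ | P(both) | P(exactly one), formula | P(exactly one), simulated t tests |
|---|---|---|---|
| 0 | 0.640 | 0.320 | 0.320 |
| 0.5 | 0.687 | 0.226 | 0.230 |
| 0.7 | 0.713 | 0.174 | 0.178 |
| 0.9 | 0.750 | 0.100 | 0.103 |

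If no patient were lost (19 per group) and the effect were the same, the simulated figures would be 19.3%, 15.1% and 8.7% at ρ = 0.5, 0.7 and 0.9.

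**5. Is baseline adjustment worth writing in?** With equal variances at baseline and follow-up, and correlation r between them, the residual variance after adjustment is (1 + r)/2 times that of the change score. At r = 0.9 the ratio is 0.95 and the standardised effect becomes 0.99/√0.95 = 1.02. At r = 0.3 the ratio is 0.65 and the effect becomes 0.99/√0.65 = 1.23. In a check on normal data, power rises from about 80% to 81% and 93% respectively. These figures are for the ordinary adjusted test; the rank-based form was not calculated here.

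**The case against.** The strongest reply is that 10% to 23% disagreement is a property of any two correlated tests with about 80% power each, and that naming a visit would not lower it. That is right. The figure shows how often the missing rule would be needed; it is not itself an error rate. The inflation of the false-positive rate is the measurable harm, and it arises only under an either-visit reading.

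A second reply is that the between-arm comparison is obviously the main one. This also stands. Arm/Group Information randomises patients to the two arms, and the Overall Limitations and Caveats entry describes the study as a comparison of two treated groups. Nothing says that a paired test within one arm shows efficacy. But this leaves two between-arm comparisons, unranked.

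A third reply is that the repeated-measures ANOVA in the sizing sentence implies one test across visits. Such a test could have removed the ambiguity, but it is not carried into the listed analyses, and the effect it would test is not stated.

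Four stronger readings are tempting, and the documents do not support them:

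- *The plan declares success if either visit is significant.* It is silent on this.
- *Power is below 80%.* The missing ANOVA inputs are a reporting gap and show nothing about the power achieved.
- *The trial was sized at an error rate of 0.05%.* The same section later sets 0.05, so the percentage sign is an evident slip.
- *An 80% interval is planned for FOIS.* The entry sits in a generic results-form table and may be only a form selection.

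**Conclusion.** The concern holds in a limited form. The deciding follow-up for the sole primary outcome is not named, no test is explicitly assigned to FOIS, and there is no multiplicity rule. This should be settled before FOIS is compared by arm, because a rule chosen afterwards cannot remove the freedom to choose.

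The possible inflation, from 5% to between 7.0% and 9.1%, is conditional on either visit being accepted as success. The 10% to 23% guide figure further assumes 17 per group and equal 0.99 SD effects at both visits. Both ranges rest on assumed correlations and are illustrative. The gap in the text depends on none of these assumptions.

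**What to change.** Amend the Statistical Analyses section before any comparison of FOIS by arm:

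1. Name one of the two existing follow-ups as primary. Make the primary analysis a single between-arm test of FOIS at that visit, adjusted for the baseline FOIS already collected, in rank-based form because the scale has seven ordered levels.
2. Test the other follow-up at 0.05 only if the first is significant. This fixed order keeps the overall error rate for the two visits at 5%.
3. State that the paired tests within each arm are descriptive.
4. Correct the 0.05% in the sample-size sentence to 0.05 (5%).
5. Report the primary between-arm result with a 95% interval for the effect measure that goes with the chosen test. Reconcile this with the Measure of Dispersion/Precision entry, since an 80% interval does not match a 0.05 level.

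The change is wording only and adds no patients, visits or measurements. Its downside is that an effect present only at the non-primary visit would not be formally tested. As a guide, for unadjusted t tests with 17 per group and 0.99 SD at both visits, the fixed order keeps 80% power at the named visit and gives 68% to 75% for both (ρ from 0.5 to 0.9). These figures are not for the rank-based adjusted test recommended here.

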## **Secondary Outcome Measures:**

- Change in Eating Assessment Tool-10 (EAT-10) Score

Eating Assessment Tool-10 (EAT-10) is used to assess participants' dysphagia symptoms, symptom severity, and risk of oropharyngeal dysphagia. This scale is a scale of 10 questions that the patient himself answers, which questions the symptoms of dysphagia. The answer points for each question range from 0 (no problem) to 4 (serious problem). If EAT-10 score is  $\geq 3$ , it is considered as "risk of oropharyngeal dysphagia". It is a useful tool to evaluate the severity of dysphagia symptom in the clinic, to monitor the progression and effectiveness of the disease.

[Time Frame: before intervention, immediately after intervention, 3 months after the intervention]

- Change in Swallowing-related Quality of Life (SWAL-QOL) Score

Swallowing-related quality of life scale (SWAL-QOL) is used to evaluate the effect of swallowing disorders on quality of life. It was created to evaluate the quality of life of patients with oropharyngeal dysphagia. It includes a total of 44 questions under eating disorder, eating time, eating desire, food selection, communication, anxiety, mental health, social functionality, fatigue, and sleep subgroups. Each question is evaluated with a score ranging from 1 (worst) to 5 (best). The subgroup scores of the scale and the total score of the scale can be used to assess the change in patients.

[Time Frame: before intervention, immediately after intervention, 3 months after the intervention]

- Change in Visual Analog Scale (VAS)

Patients' difficulty in swallowing will be questioned using the Visual Analogue Scale (VAS). On a scale of ten centimeters, patients will be asked to mark the appropriate level of dysphagia 0: No dysphagia, 10: Very severe dysphagia.

[Time Frame: before intervention, immediately after intervention, 3 months after the intervention]

- Change in Laryngostroboscopy Examination

In the Istanbul Faculty of Medicine Otorhinolaryngology Diseases Clinic, evaluations will be made by the Ear Nose Throat Specialist. Whether there is vocal cord paresis and paralysis and whether glottic patency is evaluated in the laryngostroboscopic examination.

[Time Frame: before intervention, immediately after intervention]

- Change in Fiberoptic Endoscopic Evaluation of Swallowing (FEES)

FEES will be performed by the otolaryngologist doctor before and immediately after the treatment. In the fiberoptic endoscopic swallowing assessment, the condition of the patient according to the penetration aspiration scale will be checked. Grade 1 represents the best and grade 7 the worst on the penetration aspiration scale.

[Time Frame: before intervention, immediately after intervention]

- Change in Voice-Related Quality of Life (V-RQOL) Score

This ten-item scale is a scale designed for adult populations with voice disorders to measure both social-emotional and physical-functional aspects of voice problems. The answer points for each question range from 1 (few problems) to 5 (serious problems). A total score change on this scale will be used to evaluate patients.

[Time Frame: before intervention, immediately after intervention, 3 months after the intervention]

Arms	Assigned Interventions

Experimental: Neuromuscular Electrical Stimulation (NMES) with TDT
	
Device: Procedure: Neuromuscular Electrical Stimulation with TDT
 
The skin to be treated will be cleaned and dried. NMES will be implemented with signals received from two channels. In the first channel, the upper electrodes will be placed horizontally just above the hyoid bone. This is the place where the cupping is felt when the finger is pressed right under the chin. In the second channel, the lower electrodes will be placed horizontally, just above the thyrohyoid muscle. This is the place where you can feel a cupping when pressed with your finger, on both sides of the apple in the larynx. The device will be set to start at the lowest power, with very short pulses of approximately 700 microseconds, at intervals of 1 second. The power will be gradually increased according to the device and the power that the patient feels vibration will be stopped. The power to be applied will not exceed 25 milliamps. NMES application and Traditional Dysphagia Therapy will be applied for 45 minutes a day, 5 days a week for 3 weeks.


Active Comparator: Traditional Dysphagia Therapy (TDT)
	
Behavioral: Procedure: Traditional Dysphagia Therapy (TDT)
 
Traditional dysphagia therapy includes diet modification training, teaching postural compensatory methods, training of oral motor control exercises and tongue root exercises, training of swallowing maneuvers, and practice of chin-resistance exercise, which is the exercise of opening the upper esophageal sphincter.
 
Traditional Dysphagia Therapy will be applied for 45 minutes a day, 5 days a week for 3 weeks.

## Analysis Population Information

### Overall Number of Participants Analyzed \*

A total of 38 patients were planned to be included in the study.

### Type of Units Analyzed [\*]

The analysis will be based on participants.

## Outcome Measure Data Table

### Measure Type \*

Count of Participants

### Measure of Dispersion/Precision \*

80% Confidence Interval

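### The outcome table's single participant-count measure type and its unexplained 80% interval do not match the analysis text (minor, reporting only)

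*Combined protocol and SAP*

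**What the plan says.** In the Combined protocol and SAP, section 3 (Outcome Measures), the Outcome Measure Data Table has a Measure Type entry of "Count of Participants" and a Measure of Dispersion/Precision entry of "80% Confidence Interval". Each appears once, with no outcome named.

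The outcomes they cover are mostly scores. For the primary outcome, "The change in FOIS will be our primary outcome measure in our research", on a scale of 7 ordered levels, with time frame "before intervention, immediately after intervention, 3 months after the intervention". EAT-10, SWAL-QOL, VAS and V-RQOL are also changes in score; for SWAL-QOL, "The subgroup scores of the scale and the total score of the scale can be used to assess the change in patients". Two outcomes differ in kind: laryngostroboscopy records the presence or absence of findings, and FEES is graded on a penetration aspiration scale.

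The Statistical Analyses text separates the two kinds of variable. For scores and other measurements it plans this: "Descriptive statistics of numerical variables will be given as mean, standard deviation, median, minimum and maximum". Categorical findings are handled in another way: "Descriptive statistics of qualitative variables will be given as numbers and percentages". It compares groups by t or Mann-Whitney tests and says "A statistical significance level of 0.05 will be taken". It does not state whether tests are one-sided or two-sided, plans no confidence interval, and gives no reason for 80%.

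**The concern.** Two entries that apply to every outcome do not agree with the analysis text. A participant count is not how that text summarises numerical variables, and an 80% interval does not go with a 0.05 test.

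What is at stake is how results are presented. If the table is filled in as written, the score outcomes need categories that nobody has defined in advance, and those categories could be chosen after the data are seen. If the 80% interval is attached to a treatment comparison, a non-significant result can appear beside an interval that excludes zero, and a reader may take the interval as evidence of benefit.

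**Working it through.** **Inputs from the Statistical Analyses text.** Significance level 0.05; 17 per group required; 19 per group planned after a 10% allowance for exclusions (17/0.90 = 18.9, so 19, which reproduces). Sidedness is not stated. The true effect, the SD and the place where the interval would be used are not given, so anything that depends on them is an assumption.

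**Step 1: can 80% be derived from the stated level?**
- Two-sided 0.05: 1 − 0.05 = 95%.
- One-sided 0.05: 1 − 2 × 0.05 = 90%.
- The sample-size sentence prints the type I error as 0.05%. Taken literally, this gives 1 − 0.0005 = 99.95% two-sided or 99.90% one-sided.
- In reverse, an 80% interval corresponds to a two-sided level of 0.20, or a one-sided level of 0.10.

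No reading gives 80%.

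**Step 2: how much narrower is it?** For a two-sample t interval the half-width is t × √(2/n), in units of the SD of the change score, with 2n − 2 degrees of freedom.

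| n per group | df | t for 80% | t for 95% | Ratio | Half-width, 80% | Half-width, 95% |
|---|---|---|---|---|---|---|
| 17 | 32 | 1.309 | 2.037 | 0.642 | 0.449 SD | 0.699 SD |
| 19 | 36 | 1.306 | 2.028 | 0.644 | 0.424 SD | 0.658 SD |

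The 80% interval is about 36% narrower. The same holds in kind for a count. With an assumed 9 of 17 participants in some category, the exact (Clopper-Pearson) 80% interval is 35.0% to 70.3% and the 95% interval is 27.8% to 77.0%. The width ratio is 0.716, so the 80% interval is 28% narrower.

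**Step 3: conditional illustration.** Suppose the 80% interval is a two-sided t interval on the between-arm difference in change. The plan does not say this. The interval excludes zero while p is above 0.05 when |T| lies between the two multipliers in step 2. T is noncentral t with noncentrality d × √(n/2), where d is the true difference in SD units. With no effect the probability is 0.20 − 0.05 = 0.15. Over assumed values of d:

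| d | 0 | 0.2 | 0.4 | 0.5 | 0.6 | 0.8 | 1.0 |
|---|---|---|---|---|---|---|---|
| 17 per group | 0.150 | 0.184 | 0.251 | 0.273 | 0.277 | 0.228 | 0.138 |
| 19 per group | 0.150 | 0.188 | 0.257 | 0.275 | 0.272 | 0.206 | 0.111 |

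The peaks are 0.278 (d = 0.57) and 0.277 (d = 0.54), so the range is 11% to 28%.

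**Step 4: which outcomes does a count fit?**
- Laryngostroboscopy findings: yes, and this agrees with the planned summary for qualitative variables.
- EAT-10, SWAL-QOL, VAS and V-RQOL score changes: poorly.
- Change in FOIS: usable only as counts by level or by change category, and no categories are defined.
- FEES penetration aspiration grade: the plan does not say whether it is treated as a score or as categories.

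**The case against.** The strongest reply is that these are form entries and not the analysis plan. The document is laid out as registry results data elements, and the baseline section is just as generic: it also enters a participant count although it selects continuous age. The operative text is Statistical Analyses, which describes numerical variables properly and decides by p < 0.05. This stands as a limit on importance. It does not remove the conflict, because the 80% entry is the only precision the document states for the outcomes.

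The second reply is that an 80% interval is valid at its own level. That is correct. The fault is the unexplained mismatch with 0.05.

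Several stronger readings are tempting and are not supported:

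- **That the table could show no size of FOIS change.** FOIS is ordinal, and counts by change category would show size. What is missing is the definition of the categories.
- **That the interval contradicts the p-value.** This needs the interval to sit on the between-arm difference. The entries belong to the outcome data table, while the group comparison is described under its own heading, which plans no interval. An interval on each arm's own summary does not contradict the between-group test, although it is still narrower than one at the 0.05 level.
- **That the trial in effect tests at 0.20.** No decision rule uses the interval.
- **That 80% was carried over from the 80% power.** The figures coincide, but nothing in the document shows a mix-up.
- **That a count with an interval breaks the document's own pairing.** The baseline section allows dispersion to be marked as not applicable for counts. It does not forbid an interval, and it concerns baseline only.

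**Conclusion.** The concern holds as a minor, reporting-only inconsistency. The blanket count disagrees with the analysis text for the numerical outcomes, and for FOIS it is incomplete without defined categories. The 80% level follows from no reading of the stated significance level and describes no named estimate.

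The firm figure is the width: about 36% narrower than 95% for a t interval at 17 or 19 per group. The 15% under no effect and the 11% to 28% range are illustrations. They rest on three assumptions: placement on the between-arm difference, two-sided t intervals, and true differences of 0 to 1.0 SD. The 0.05 tests, type I error and sample size are unaffected.

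**What to change.** **Measure Type.** Enter mean or median change for the numerical score outcomes, including FOIS, in line with the Statistical Analyses text. Keep counts for categorical results such as laryngostroboscopy. State which type applies to the FEES penetration aspiration grade.

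**Measure of Dispersion/Precision.** Replace 80% with a two-sided 95% confidence interval and name the estimate it describes.

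**Optional.** Add an interval for the between-arm difference in FOIS change at the end of treatment and at the three-month visit. This would be a new output, since none is planned, and correcting the two entries does not depend on it.

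**Cost.** Two table entries and a sentence naming the estimate. Reported t intervals become about 56% wider at 17 per group (2.037/1.309 = 1.56) and 55% wider at 19 (2.028/1.306 = 1.55). Sample size and the 0.05 tests stay as they are.
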